**Impact of DNA fragmentation in sperm on the pregnancy outcome after
intra-uterine insemination in a spontaneous cycle**

NCT03319654

Document date: September 7th 2017

Introduction

Infertility affects about 10% of all couples and is defined by a failure to achieve a clinical pregnancy within a year of regular unprotected sexual intercourse. (Boivin 2007, Zegers-Hochschild 2009).

Male infertility accounts for nearly 30% of diagnoses, whilst an estimated 40% of male factor infertility remains unexplained (de Kretser 1997) and most of male factor infertility cannot be treated adequately.

The current diagnosis of male infertility is based on semen criteria updated by the WHO in 2010. These guidelines would consider a man normal with reference values of greater than 15 million sperm, greater than 4% normal morphology, and 32% progressive motility. By doing so more men are considered fertile while there may be an unnoticed rise in the number of infertile men meantime being assigned to the ‘unexplained’ category. Furthermore , although the WHO classification suggests accuracy through a methodology harmonized across laboratories (Wang 2014), the relevance for the choice of treatment and the predictive value for an infertile couple embarking on medically assisted reproduction technologies (MAR) is questionable. (Hamilton 2015)

In other words, there is a strong clinical need to distinguish fertile from infertile men through new sperm function testing and to be able to select both the patient population who will benefit from MAR as well as the type of treatment.

Numerous studies utilizing different techniques for assessing sperm DNA fragmentation support the existence of a significant association between sperm DNA damage and pregnancy outcomes (Collins et al., 2008). Moreover, a significant number of subfertile men have abnormal DNA integrity despite normal semen parameters (Kodama et al., 1997; Spano et al., 2000; Zini et al., 2001). The level of DNA fragmentation correlates negatively with pregnancy and delivery in both natural and assisted conceptions (Evenson & Wixon 2006; Zhang et al. 2008; Zini 2011).

Our laboratory has set up a program where direct DNA fragmentation testing with terminal deoxyuridine nick end labeling (TUNEL) assay (Mitchell 2011) on fresh samples was established both on the total and vital fraction, before and after density gradient. The data results have been submitted and will be available soon (Punjabi 2017).

In this prospective cohort study we aim to investigate the role of sperm DNA fragmentation analysis in selecting the patient who will benefit from intra-uterine insemination (IUI) therapy since IUI is still considered the first step in MAR and is performed at a large scale in Belgium and worldwide.

The overall success rate of IUI remains controversial. On average, reported clinical pregnancy rates are only 5–13% per IUI cycle (Bensdorp et al., 2007; Goverde et al., 2000; Guzick et al., 1999; Nyboe Andersen et al., 2009; Steures et al., 2004, 2007; The ESHRE Capri Workshop Group, 2009; Tummon et al., 1997; Verhulst et al., 2006).

A Cochrane analysis pointed to the position of IUI in male subfertility treatment as being one of the most frequently used treatments (Veltman-Verhulst et al., 2016) although its efficacy in the setting of mild male/unexplained infertility is yet to be proven. The authors concluded that there was insufficient evidence of effectiveness to recommend or advise against IUI.

In addition, the literature pertaining IUI consists of a broad range of indications for therapy, ranging from but not limited to: unexplained fertility, mild male infertility and mild endometriosis. Respectively, each of these diagnoses also have slightly different definitions from one study to another, thus making a univocal recommendation concerning IUI very challenging.

Our goal would be to better select patients for IUI, widely considered less invasive and expensive therapy than others, as about 50% of the patients entering an IUI program will not become pregnant after 4-6 IUI cycles and thus in selected cases (Van Hoof et al., 2009) progression to more advanced fertility therapy could be beneficial.

Study Objectives

The objective is to test the hypothesis that DNA fragmentation testing can play a diagnostic and thus pivotal role in selecting the patient who will benefit from intra-uterine insemination (IUI) therapy leading to a higher clinical pregnancy and live birth rate (primary outcomes) compared to the standard semen criteria.

Additionally, DNA fragmentation will be measured both at the time of the diagnostic work-up as at the time of insemination with evaluation in the neat and washed specimen, both in the total and vital fraction. We aim to assess whether density gradient retrieves high quality motile sperm with little DNA damage and where DNA fragmentation testing best fits in the clinical patient pathway (secondary outcomes).

Study Endpoints

Primary outcomes:

- DNA fragmentation as a predictor of clinical pregnancy and live birth rate

Secondary outcomes:

- DNA fragmentation in the total and vital fraction before and after density gradient in the diagnostic sample (pre-IUI)
- DNA fragmentation in the total and vital fraction before and after density gradient in the therapeutic sample (IUI sample)
- DNA fragmentation in relation to the cumulative clinical pregnancy and live birth rate

Study Phase & Design

Prospective interventional study
Duration: 24 months

Source population: couples with unexplained, mild male infertility, mild endometriosis defined by revised American Society for Reproductive Medicine stage I and II

Single center, university setting, no commercial affiliation

Study Population

Inclusion criteria:

Couples seeking fertility treatment after at least 12 months of unprotected intercourse are eligible. All couples underwent basic fertility investigations which included semen analysis, evaluation of menstrual cycle, and tubal patency testing (Chlamydia antibody test, hysterosalpingography/HyfoSy or laparoscopy).

All participating couples should provide written informed consent

Inclusion criteria are

- Unexplained infertility
 - o We classify couples as having unexplained subfertility when the fertility investigations showed at least one patent fallopian tube, a normal ovulatory

- menstrual cycle (26-32), and a normal semen analysis (pre-wash total motile sperm count above 10 million).
- Mild male infertility defined as one or more abnormal semen parameters according to the WHO 2010 criteria on at least two examinations; diagnosis is determined by most abnormal result
- Women: age between 18 and 40 years, BMI between 18,5-30, presence of at least one patent tube on hysterosalpingography/Hysterosalpingo foam sonography (Hyfosalpingo) and/or laparoscopy, normal uterine cavity (ultrasound, hysterosalpingography or laparoscopy), regular menstrual cycle (24-38 days, FIGO recommendations 2011)
- Men: age between 18 and 65 years, BMI between 18,5-30, normal semen analysis or mild male subfertility
- Exclusion criteria: double sided tubal disease, severe endometriosis (classified as revised American Society for Reproductive Medicine stage III or IV), premature ovarian failure, and known endocrine disorders (such as Cushing's syndrome or adrenal hyperplasia), azoö- or necrozoöspermia

Statistics

- Sample size: 120 patients
A power analysis was performed to estimate the sample size needed for ROC curve analysis. Since there is scarce literature for sperm DNA fragmentation on an IUI sample both before and after gradient, we cannot rely on reference values to estimate the area under the curve (AUC) or distribution of cases versus controls (kappa). In function of a significance of 0,05 (type I error) and power of 0,8 (1-type II error), a kappa varying between 1:1 and 1:3 and AUC varying between 0,7-0,75 we estimate a minimum of 38 patients and a maximum of 130 patients should be included.
- Diagnostic parameters: sensitivity, specificity, area under receiver operator curve, predictive value, likelihood ratio, odds ratio
- Null hypothesis:
 - 1) There is no correlation between DNA fragmentation and clinical pregnancy/live birth after IUI
 - 2) Density gradient isn't capable of selecting motile sperm with low DNA fragmentation for insemination

Clinical protocol

- IUI in a spontaneous cycle
- Basal ultrasound and hormonal analysis on cycle day 2 or 3 (estradiol (E2), progesterone (P), luteinizing hormone (LH) as well as follicle stimulating hormone (FSH))
- Cycle monitoring from D10-12 with ultrasound and/or hormonal analysis (E2, P, LH)
- 250 microgram hCG or 5000 IU is administered to induce ovulation when a maximum of 2 dominant follicles are present. Either Pregnyl, Choragon, Ovitrelle will be used
- IUI is planned between 32-40 hours after HCG administration or \pm 24-26 hours after detection of spontaneous LH surge
- Both ultrasound and hormonal analysis (E2, P, LH) are done on the day of planning of IUI (day of hCG administration or day of LH surge)
- Sperm preparation is performed according to local validated procedures in accordance with the 2010 WHO criteria. DNA fragmentation analysis by TUNEL assay will be carried out both before and after density gradient.
- Patients are advised to rest in the supine position during 15 minutes immediately after IUI according to evidence from a RCT (Custers et al. 2009)
- Detection of pregnancy
 - β HCG testing is performed 15-20 days after insemination
 - A second β HCG testing is performed 7 days later to confirm a positive evolution of pregnancy
 - In case of a positive evolution of β HCG an ultrasound is performed around 5-6 weeks after IUI
 - Follow-up of pregnancy until birth through staff, telephone or e-mail contact until birth

- Items to be registered
 - Number of eligible patients (patients who fulfilled inclusion criteria and to whom the study was proposed)
 - Number of drop outs between inclusion and end of treatment
 - Number of spontaneous pregnancies between inclusion and end of treatment
 - Number of live births between inclusion and end of treatment

 - Hunault score and modified Hunault-score according to Bendsorp et al.
 - All Belrap items
 - Semen analysis methodology checklist according to Björndahl et al. (Appendix)
 - Patient population characteristics:
 - Infertility: duration, primary versus secondary, female/male/mixed/unexplained
 - Cause of female infertility: Ovulatory disorder, Anatomical infertility, Endometriosis (revised American Society for Reproductive Medicine classification) or Adenomyosis
 - Possible cause of male infertility: Varicocele, Cryptorchidism, Male accessory gland infections, Germ cell malignancies and testicular microcalcifications, Disorders of ejaculation, Idiopathic. Primary spermatid failure, genetic disorders of infertility, obstructive azoospermia, hypogonadism were not reported since azoospermia is considered an exclusion criterium.

- Data analysis and Publication policy
Data analysis and preparation for publication will be done at the University Hospital of Antwerp / University of Antwerp.

References

de Kretser DM. Male infertility. *Lancet.* 1997; 15: 349(9054):787-790.

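### No analysis by indication is planned, so a weak pooled AUC could partly repeat the unexplained/mild-male split already made by the semen criteria instead of showing value beyond them

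*Combined protocol and SAP*

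**What the plan says.** The Introduction notes that published IUI studies cover many indications and that each diagnosis is defined somewhat differently between studies, "thus making a univocal recommendation concerning IUI very challenging". Study Phase & Design then names the cohort: "Source population: couples with unexplained, mild male infertility, mild endometriosis" (revised ASRM stage I and II).

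Study Objectives sets the aim: fragmentation testing should select couples who benefit from IUI, with the standard semen criteria as comparator. Under Study Population, unexplained infertility requires a normal semen analysis, and mild male infertility is defined by abnormal WHO 2010 parameters.

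Statistics gives one sample size (120), one ROC power calculation and one list of measures: "sensitivity, specificity, area under receiver operator curve, predictive value, likelihood ratio, odds ratio". Null hypothesis 1 is that fragmentation and pregnancy or live birth after IUI are uncorrelated. No stratification, adjustment or subgroup analysis is mentioned.

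Under Items to be registered, the infertility diagnosis is recorded ("duration, primary versus secondary, female/male/mixed/unexplained"), with endometriosis as a separate cause field. Both are listed as population characteristics, with no role in the analysis.

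**The concern.** A pooled AUC compares every conceiving couple with every non-conceiving couple, including pairs from different indications. Mild male couples are defined by their semen, so their fragmentation may run higher; their chance of pregnancy may also differ. Where both hold, a pair such as a conceiving unexplained couple and a non-conceiving mild male couple can be ranked correctly only because fragmentation has recovered the diagnosis. The clinic knows that diagnosis from the semen analysis, which is the stated comparator.

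At stake is the conclusion. A modest AUC above 0.5 could be read as added value over the semen criteria when it is not. The Introduction argues that abnormal DNA integrity can accompany normal semen parameters. That is a claim about information inside an indication, and the pooled figure does not isolate it. Pooled predictive values would likewise average over indications if pregnancy rates differ.

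**Working it through.** **1. The plan's own figure.** Statistics gives 38 to 130 patients for "a kappa varying between 1:1 and 1:3 and AUC varying between 0,7-0,75", at a type I error of 0.05 and power of 0.80. Assume a two-sided test against AUC 0.5 and the Obuchowski binormal variance V = 0.0099·exp(−a²/2)·[(5a²+8) + (a²+8)/k], with a = 1.414·z(AUC) and k controls per case. Cases needed = [1.96·√V₀ + 0.842·√V₁]² / (AUC−0.5)².
- AUC 0.75, 1:1: V₀ = 0.158, V₁ = 0.135, giving 19 cases and 19 controls, total 38. The minimum reproduces.
- AUC 0.70, 1:3: 21 cases and 63 controls, total 84 (88 with the Hanley–McNeil variance). The maximum of 130 does not reproduce. That is a separate matter and does not affect this point.

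The calculation treats the cohort as one group.

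**2. Pooled AUC when fragmentation is uninformative inside each indication.** Take two indications, with fragmentation normal with equal SD in each. Let m be the mild male share, δ their upward shift in SD, and p_U and p_M the pregnancy probabilities in unexplained and mild male couples. The mild male share is
- among conceiving couples: c = m·p_M / [m·p_M + (1−m)·p_U]
- among non-conceiving couples: d = m(1−p_M) / [m(1−p_M) + (1−m)(1−p_U)]

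Pooled AUC = 0.5 + (d − c)·[Φ(δ/√2) − 0.5]. It leaves 0.5 only if d ≠ c (pregnancy rates differ) and δ ≠ 0 (fragmentation differs).

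The document gives neither quantity by indication. The values below are assumptions: m 30–50%, δ 0.5–1.0, p_U 50–55%, p_M 25–40%. They are cumulative-type rates, in line with the Introduction's figure of about half of couples not pregnant after 4–6 cycles.
- Low end (m 0.3, δ 0.5, 50% v 40%): c = 0.255, d = 0.340; AUC = 0.5 + 0.084 × 0.138 = 0.51.
- Middle (m 0.5, δ 0.8, 50% v 30%): c = 0.375, d = 0.583; AUC = 0.5 + 0.208 × 0.214 = 0.545.
- High end (m 0.5, δ 1.0, 55% v 25%): c = 0.3125, d = 0.625; AUC = 0.5 + 0.3125 × 0.260 = 0.58.

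**3. Rejection by the pooled rank test at N = 120.** The null SD of the AUC is √[(n₁+n₂+1)/(12·n₁·n₂)]. The middle and high cases both expect 120 × 0.40 = 48 pregnancies, so SD = √[121/(12×48×72)] = 0.054.
- Middle: 0.0446/0.054 = 0.83, giving about 13% rejection.
- High: 0.0813/0.054 = 1.5, giving about 32–33%.
- Low: about 5%.

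Simulation agrees, with 5–33% over the assumed range. A van Elteren test stratified by indication stays at 4–6%.

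**4. Where the effect shrinks or reverses.**
- Equal pregnancy rates: d = c, so AUC is 0.50 and rejection 5%.
- Per-cycle rates (13% v 5%, m 0.4): c = 0.020/0.098 = 0.204, d = 0.380/0.902 = 0.421. At δ = 1 the AUC is 0.5 + 0.217 × 0.260 = 0.56. Only 120 × 0.098 ≈ 12 pregnancies are expected, and simulated rejection over δ 0.5–1.0 is roughly 6–9%. At 10% v 7% it is 5–6%. The shift persists, but the test has little power to detect it.
- Three indications (40/40/20% unexplained, mild male, endometriosis; 1 SD shift in mild male): pooled AUC 0.54 at pregnancy rates of 60/40/50%, and 0.46 if mild male couples do better (40/60/50%). The direction cannot be known beforehand.

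**5. Could mix alone produce the design AUC?** At the high end, (0.70 − 0.581)/0.054 = 2.2, so an observed AUC of 0.70 or more occurs in about 1% of trials. At 13% v 5% per cycle, SD = √[121/(12×11.76×108.24)] = 0.089 and (0.70 − 0.557)/0.089 = 1.6, about 5%, much of it sampling noise from so few pregnancies.

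**6. Price of stratifying.** With a true within-indication AUC of 0.70, the SD of the stratified AUC is 0.048–0.050, against 0.047–0.049 pooled. Simulated stratified power at N = 120 is 0.96 with about 50% pregnant, 0.91 at 25% and 0.57 at 5–13%.

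**The case against.** Several objections have force.

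- A reader might infer that the protocol itself says these three indications cannot share one recommendation. It does not. The Introduction describes the literature and blames differing definitions between studies as well as the range of indications. Pooling is also inferred from silence, although no other analysis is described.
- A reader might call the 5–33% a false-positive rate for null hypothesis 1. That null is marginal. If indication mix creates an overall association, the null as worded is false and rejecting it is correct. The error lies in reading the rejection as information beyond the semen criteria.
- A test meant to replace a semen-based label need not be conditioned on that label, and the Introduction does question the predictive value of the WHO classification. The pooled AUC therefore answers a legitimate question and need not give way as the main result.
- Every size rests on assumed differences by indication.
- A reader might also say that pooling hides a real effect. The shift found is trivial: 0.70 becomes 0.69 with equal pregnancy rates and a 0.8 SD shift.
- The stratifying variable is not ready. The registered categories include a mixed group, endometriosis sits in another field, and the Study Population definitions overlap: a couple can have a total motile count above 10 million and one abnormal WHO parameter.

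All of this stands. It narrows the point to what may be claimed against the comparator, and it adds a task to the fix. It does not remove the gap, because semen results define the split that the pooled AUC can absorb.

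**Conclusion.** The point holds in a limited form. As written, the accuracy analysis is pooled over indications that the semen criteria already distinguish, so a weak positive AUC cannot be taken as value beyond those criteria. Under the assumed differences, mix alone moves the AUC by 0.01–0.08. Inflation is little or absent when pregnancy rates are equal or at the per-cycle rates cited in the Introduction. A result at the design AUC would be hard to explain by mix alone. The documents do not support reading this as an invalid test of the stated null hypothesis or as a reason to drop the pooled AUC. It should be addressed, because it bears directly on the stated objective and the diagnosis data are already to be collected.

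**What to change.** In Statistics:
- Keep the pooled AUC. Prespecify beside it an indication-stratified AUC (conceiving against non-conceiving couples within the same indication, combined across strata) with a van Elteren test.
- State that any claim of value beyond the semen criteria rests on the stratified result.
- Define one stratum per couple from the registered fields. Say where mixed and mild endometriosis couples go, and how a couple meeting both semen definitions is assigned.
- Report accuracy measures by indication with confidence intervals, as description only.

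The cost is a short addition to the text, an allocation rule fixed before outcomes are analysed, and a little more analysis. No extra couples or data items are needed. The downsides are wide intervals within an indication, especially at per-cycle rates (5–13% of 120 is about 6–16 pregnancies in all), and an endometriosis stratum that, if small, adds little.

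### The objective claims to identify who benefits from IUI and to raise pregnancy rates; the design can show only prognosis after IUI

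*Combined protocol and SAP*

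**What the plan says.** The Introduction describes the study as follows: "In this prospective cohort study we aim to investigate the role of sperm DNA fragmentation analysis in selecting the patient who will benefit" from IUI. The Study Objectives section repeats the aim as a hypothesis about "selecting the patient who will benefit from intra-uterine insemination (IUI) therapy leading to a higher clinical pregnancy and live birth rate", with the comparison made "compared to the standard semen criteria". The Introduction also gives the intended use. About half of couples are not pregnant after 4-6 IUI cycles, so in selected cases "progression to more advanced fertility therapy could be beneficial".

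The working parts of the plan are narrower. Study Endpoints makes fragmentation a predictor of clinical pregnancy and live birth. The first null hypothesis under Statistics reads "There is no correlation between DNA fragmentation and clinical pregnancy/live birth after IUI". The planned measures are sensitivity, specificity, AUC, predictive value, likelihood ratio and odds ratio, and the sample size is for a ROC analysis. The Clinical protocol describes IUI in a spontaneous cycle and no other treatment.

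Two statements in the Introduction bear on what *benefit* can mean here. On IUI in mild male or unexplained infertility: "its efficacy in the setting of mild male/unexplained infertility is yet to be proven". On the marker: "The level of DNA fragmentation correlates negatively with pregnancy and delivery in both natural and assisted conceptions".

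**The concern.** Benefit from a treatment is the difference between the outcome with it and the outcome without it, or with an alternative. A marker that separates good from poor outcomes among treated couples is prognostic. It identifies who benefits only if the outcome without treatment does not vary with the marker in a way that accounts for the separation. The plan has no comparison treatment and no management by test result, yet its objective is worded as if both claims were under test.

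What is at stake is interpretation. If the first null hypothesis is rejected and the result is read through the present objective, it could be taken to show that couples with low fragmentation gain more from IUI, or that selecting on the test increases pregnancies. The data would support neither statement.

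**Working it through.** **1. What each part of the plan can deliver.**

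| Part of the plan | Quantity it concerns |
|---|---|
| Study Objectives | Who gains from IUI; higher rates through selection |
| Study Endpoints, primary | Prediction of pregnancy and live birth |
| Statistics, null hypothesis 1 | Association with outcome after IUI |
| Statistics, diagnostic parameters | Discrimination and accuracy among treated couples |
| Clinical protocol | One treatment, IUI; no allocation by test |
| Items to be registered | "Number of spontaneous pregnancies between inclusion and end of treatment", with no analysis attached |

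Only the first row needs an outcome without IUI or under a different selection rule. No row supplies one.

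**2. What benefit would require.** Let a_L and a_H be the probability of pregnancy after IUI at low and high fragmentation, and b_L and b_H the probabilities for the same couples without IUI. Then

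- prognostic difference = a_L − a_H
- benefit in each group = a_L − b_L and a_H − b_H
- differential benefit = (a_L − b_L) − (a_H − b_H) = (a_L − a_H) − (b_L − b_H)

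The study observes a_L and a_H only. The term b_L − b_H vanishes only if natural conception is unrelated to fragmentation, and the Introduction says it is related, negatively. On that statement b_L exceeds b_H, so on the absolute scale the prognostic difference overstates the differential benefit by an amount the study cannot estimate.

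**3. What selection would require.** To show that test-based selection raises the pregnancy rate, some couples must be managed by the test, and the outcomes of those directed elsewhere must be known. Neither is planned.

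**4. Illustration.** The plan gives no figure for benefit that could be reproduced. It does give 5-13% clinical pregnancies per IUI cycle, a range across published reports, and about 50% not pregnant after 4-6 cycles. Giving 13% to low and 5% to high fragmentation is an assumption. So are the cumulative rates of 60% and 40%, chosen to average 50%, and every rate without IUI.

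| Scale | After IUI, low / high | Without IUI, low / high (assumed) | Gain in points, low / high |
|---|---|---|---|
| Per cycle | 13 / 5 | 6 / 2.3 | 7 / 2.7 |
| Per cycle | 13 / 5 | 12 / 1 | 1 / 4 |
| Cumulative | 60 / 40 | 40 / 40 | 20 / 0 |
| Cumulative | 60 / 40 | 40 / 20 | 20 / 20 |
| Cumulative | 60 / 40 | 60 / 40 | 0 / 0 |
| Cumulative | 60 / 40 | 50 / 20 | 10 / 20 |

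The planned measures cannot tell these rows apart. In both per-cycle rows the odds ratio is (0.13 × 0.95) / (0.05 × 0.87) = 0.1235 / 0.0435 = 2.84. The AUC likewise uses only outcomes after IUI, so it is the same within each scale. In the first row the relative gain is equal in the two groups (13/6 = 2.17 and 5/2.3 = 2.17), so even the 7 against 2.7 points would not mean that IUI works better, in relative terms, at low fragmentation.

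**5. How extreme is the reversal?** With 13% and 5% after IUI, the larger gain moves to high fragmentation only if b_L − b_H exceeds 13 − 5 = 8 points, so b_L must exceed 8% per cycle. Eligible couples have at least 12 months without conception. At a constant 8% per cycle, 0.92^12 = 37% of couples would still be unpregnant after 12 cycles; at 12%, 0.88^12 = 22%. The 12% row is therefore an extreme case. It shows that the ranking is not identified, not that it is likely to reverse.

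**The case against.** The strongest reply is that everything operational is already prognostic: the title refers to outcome after insemination, the Introduction calls the study a cohort, and the endpoint, null hypothesis and measures follow suit. The objective compares the test with another test, the standard semen criteria, not IUI with no treatment. Since the Introduction frames the problem as couples who do not become pregnant within 4-6 cycles, *benefit* may simply mean becoming pregnant after IUI. Likewise, a higher rate may mean only that couples below a fragmentation cut-off have a higher observed rate than couples with normal semen criteria, which the cohort can describe.

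Much of this stands. It confines the fault to the objective and the aim that precedes it, and leaves the primary analysis untouched. It does not remove the fault. Even if benefit means pregnancy after IUI, a claim that selection leads to a higher rate needs couples who are selected, and there are none. The descriptive comparison is available, but it is not what the sentence says, and the plan gives no cut-off for it.

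A reader might also infer that the plan intends to withhold IUI from couples with high fragmentation. The documents do not say so. They say that progression could be beneficial in selected cases, and no planned conclusion is written down. Nor do they say that fragmentation lowers conception; they report a negative correlation.

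**Conclusion.** The point holds as a mismatch between the stated objective and the design. The cohort can estimate the prognostic value of fragmentation after IUI. It cannot show differential benefit from IUI, or that selecting by the test raises pregnancy or live birth rates. This is a matter of identification, so a larger sample would not help.

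It would go too far to conclude that the study cannot answer its primary question or that the ROC analysis is invalid: the primary outcome and first null hypothesis are answerable as written. It would also go too far to read the scenarios as evidence of size, because the documents give no pregnancy rate by fragmentation level, with or without IUI.

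The conclusion rests on the absence of any comparison treatment or test-guided management from the documents. That every enrolled couple receives IUI is an inference. Drop-outs and spontaneous pregnancies are registered, so some may not, but those couples are not set up as a comparison group. The correction should be made because it limits what the trial may conclude.

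**What to change.** Restate the objective as: *prognostic value of DNA fragmentation for clinical pregnancy and live birth in couples treated with IUI, compared with standard semen criteria*. Remove the wording about who will benefit and the clause about a higher rate, and bring the matching aim in the Introduction into line. Add a sentence that the results do not support conclusions about IUI versus no IUI or versus another treatment.

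If a statement about selection is still wanted, report the observed pregnancy rate in couples below a fragmentation cut-off beside the rate in couples with normal semen criteria. Label it descriptive and say that the two groups overlap. Either fix the cut-off in advance or correct the result for optimism, since a cut-off chosen on the same data flatters the test.

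The core change costs only wording and needs no new data; the price is a more modest claim. The optional comparison also costs the work of specifying a cut-off or an optimism correction.

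### The objective compares DNA fragmentation with the standard semen criteria, but the plan as written neither tests nor estimates that comparison

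*Combined protocol and SAP*

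**What the plan says.** The Study Objectives section puts two things in one sentence. The first is that "DNA fragmentation testing can play a diagnostic and thus pivotal role in selecting the patient who will benefit" from IUI. The second is that this selection has a consequence relative to current practice: "leading to a higher clinical pregnancy and live birth rate (primary outcomes) compared to the standard semen criteria".

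The rest of the document takes up only the first part:

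- **Study Endpoints, primary outcome:** "DNA fragmentation as a predictor of clinical pregnancy and live birth rate". The three secondary outcomes also concern DNA fragmentation only: before and after the gradient in the diagnostic sample, the same in the insemination sample, and in relation to cumulative rates.
- **Statistics, null hypothesis 1:** "There is no correlation between DNA fragmentation and clinical pregnancy/live birth after IUI".
- **Statistics, null hypothesis 2:** that the density gradient is not "capable of selecting motile sperm with low DNA fragmentation for insemination".
- **Statistics, diagnostic parameters:** "sensitivity, specificity, area under receiver operator curve, predictive value, likelihood ratio, odds ratio". No second marker is named, and no difference between markers.
- **Statistics, power analysis:** "a kappa varying between 1:1 and 1:3 and AUC varying between 0,7-0,75", from which "we estimate a minimum of 38 patients and a maximum of 130 patients should be included". There is one AUC range, with no comparator AUC, difference or correlation between markers. The planned size is 120.

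Semen analysis appears as part of the work-up that all couples had, as an entry and classification criterion, and as a methodology checklist under Items to be registered.

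**The concern.** The objective and the test do not ask the same question. Null hypothesis 1 asks whether DNA fragmentation is related to outcome at all. The objective asks whether it does better than the criteria already in use. The Introduction makes that second question the reason for the study, because it doubts the predictive value of the WHO semen classification and notes abnormal DNA integrity in men with normal semen parameters.

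If the plan is followed exactly, the comparative clause ends with neither a test nor an estimate. A significant result on null hypothesis 1 could then be reported as superiority over semen criteria, which it would not show.

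A separate gap lies in the claim of higher rates. The Clinical protocol describes one IUI pathway and no rule giving or withholding IUI on the test result. A single pathway can show that a marker predicts pregnancy. It cannot show that using the marker raises the pregnancy rate.

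**Working it through.** **1. What the stated power analysis covers.** The inputs from Statistics are alpha 0.05, power 0.80, AUC 0.70-0.75 and case ratio 1:1 to 1:3. Sidedness and the null AUC are not stated; I take two-sided and 0.5. For one AUC, with k controls per case:

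n(cases) = [1.96·√V0 + 0.8416·√V1]² / (AUC − 0.5)²

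V = 0.0099·exp(−A²/2)·[(5A² + 8) + (A² + 8)/k], where A = 1.414·Φ⁻¹(AUC). V0 takes AUC 0.5 and V1 the assumed AUC (Obuchowski binormal variance).

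- AUC 0.75, k=1: V0 = 0.1584, V1 = 0.1348. n = (0.780 + 0.309)²/0.0625 = 18.98, so 19 + 19 = **38**, the stated minimum.
- AUC 0.70, k=3: V0 = 0.1056, V1 = 0.1023. n = (0.637 + 0.269)²/0.04 = 20.5, so 21 + 63 = **84** (88 with the Hanley-McNeil variance), not 130.

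The minimum is therefore what a one-marker calculation against 0.5 gives. That the whole range was built this way is an inference.

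**2. Event counts at N=120.** The ratios 1:1 and 1:3 give 120/2 = 60 and 120/4 = 30 events. The Introduction's 5-13% clinical pregnancy per cycle gives 0.05 × 120 = 6 to 0.13 × 120 = 15.6, about 16, if the outcome is read per cycle. The documents do not settle which reading applies. Cumulative rates are a separate secondary outcome, which makes the per-cycle reading plausible.

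**3. Null hypothesis 1 when DNA fragmentation has no advantage.** From the formula above, with AUC 0.70:

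- 60 events: (0.20·√60 − 1.96·√0.1584)/√0.1451 = 2.02, power 0.978.
- 30 events: (0.20·√30 − 1.96·√0.1056)/√0.1023 = 1.43, power 0.924.

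The semen score's AUC does not enter these expressions. The rejection rate is the same whether semen analysis is worse, equal or better.

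**4. The missing comparison.** I simulated paired binormal markers with one unfitted score per side, mean shift √2·Φ⁻¹(AUC) in cases, correlation 0.3, a two-sided DeLong test at 0.05 and 4,000 replicates per cell. The comparator AUC and the correlation are assumptions; the documents give neither.

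| Events of 120 | Null hypothesis 1 rejected, both AUC 0.70 | Size of difference test | Power, 0.70 v 0.60 | 95% CI half-width |
|---|---|---|---|---|
| 60 | 97% | 5% | 39% | 0.12 |
| 30 | 93% | 5% | 30% | 0.13 |
| 16 | 78% | 6% | 22% | 0.17 |
| 6 | 47% | 9% | 16% | 0.26 |

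Repeat runs differ by up to about three percentage points.

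Sensitivity, with 60/30 events:

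- 0.70 v 0.60 at correlation 0: power 29%/24%. At correlation 0.5: 49%/39%.
- 0.70 v 0.55 at correlation 0.3: 69%/58% (0.694/0.575).
- 0.75 v 0.60 at correlation 0.3: 72%/62% (0.718/0.615).

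**5. Why the semen side must not be fitted on the same couples.** Three pure-noise predictors, fitted by logistic regression and scored on the same 120 couples, show a mean apparent AUC of 0.58 (60 events) or 0.60 (30 events).

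**The case against.** **The data for a comparison exist.** This stands. All couples had semen analysis, and the listed accuracy measures are not tied to one marker, so they could be computed for semen values too. A reader might infer that the plan cannot answer the comparative question. The documents do not support that; they show that the comparison is not pre-specified or sized. The gap still matters. Semen status is defined in several ways under Study Population (a total motile count threshold, any abnormal WHO parameter, the most abnormal of at least two examinations). DNA fragmentation is measured in two samples, before and after the gradient, and in two fractions. An unplanned comparison could choose among many pairings.

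**The comparison would be imprecise, and possibly biased.** Both stand. Entry is selected on semen values and not on DNA fragmentation. A narrowed semen range can lower the semen AUC and so favour DNA fragmentation. This argues for reporting an estimate with its limits stated, not for leaving the clause unexamined.

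**That no couple is given or refused IUI on the test result is read from silence.** This is partly fair. The Introduction calls the study a cohort, while Study Phase & Design calls it interventional. However, no allocation rule or second strategy appears anywhere.

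**The maximum of 130 is a sample-size error.** A reader might infer that it undermines this point or the planned 120. It is a separate matter, and the point here does not depend on it.

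**Conclusion.** The point holds in this form: the objective contains a comparison with the standard semen criteria that the plan does not test or estimate, and rejecting null hypothesis 1 would not supply it. The textual finding rests on no assumption.

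Its size does rest on assumptions: N=120, binormal markers, correlation 0.3 and null hypothesis 1 read as AUC 0.5. With no true advantage (both AUCs 0.70), null hypothesis 1 is rejected in about 92-98% of trials with 30-60 events and about 47-78% with 6-16. Power for an assumed 0.70 versus 0.60 is about 40% (60 events), 30% (30 events) and 16-22% (6-16 events). The corresponding 95% CI half-widths are about 0.12, 0.13 and 0.17-0.26. The DeLong test's size drifts to about 6-9% at 6-16 events.

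Two stronger readings are not supported. Nothing here suggests that DNA fragmentation is no better than semen analysis; the equal-AUC case is only an illustration. Nor is the predictive question invalid, since null hypothesis 1 and the ROC measures do address it. This should be fixed before analysis, but it does not defeat the study.

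**What to change.** 1. **Reword the objective** to *prediction of clinical pregnancy and live birth by DNA fragmentation, compared with prediction by the standard semen criteria*, and remove the claim that testing leads to higher rates.
2. **Keep null hypothesis 1 and pre-specify one paired AUC difference with a 95% CI**, in the same couples and for the same outcome. One side is a single pre-named DNA fragmentation measure. The other is a single pre-named, unfitted semen score representing the WHO 2010 criteria described in the Introduction, for example the number of abnormal WHO parameters. Pre-wash total motile count can be a supporting comparator, but it is not itself those criteria. Name in advance the sample used and the direction of each score. Use a bootstrap or other small-sample interval if events are few.
3. **State the limits.** N=120 was not calculated for this difference, and the result is an estimate, not a powered test. Selection on semen values can favour DNA fragmentation, so the result must not be read as superiority outside this selected population.
4. **Confirm that the semen values are recorded.** Items to be registered names a methodology checklist and the Belrap items, but not the values.

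If the comparison is not wanted, delete the comparative clause together with the wording about higher rates.

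The cost is some rewording, two pre-named scores, one extra analysis and a check of data capture. No new patients or semen tests are needed, provided the values were captured. The price is an imprecise estimate, a coarse semen score and a more modest claim.
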